2.8.1 Adverse events

2.8.1.1 Coding of AEs

AEs will be coded using MedDRA terminology (v19.0 or later).

2.8.1.2 General rules for AE reporting

AE summaries will include all treatment-emergent AEs (TEAEs). TEAEs are defined as AEs starting on or after the first day of study treatment. All AEs will be listed. AEs starting prior to the first day of study treatment (non-TEAEs) will be flagged in the listings.

All TEAEs will be summarized by treatment phase as defined in Section 2.1.1.

TEAEs will be summarized by presenting the number and percentage of patients having at least one TEAE, having at least one TEAE in each primary SOC, and for each PT using MedDRA terminology. A patient with multiple occurrences of a TEAE will be counted only once in the AE category.

Separate summaries will be presented by SOC, PT and severity. A patient with multiple severities for an AE will be summarized under the worst severity recorded for the event.

Any information collected will be listed as appropriate.

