#### **3.1      Study design**

This study is a multicenter, randomized, double-blind, double dummy, parallel group, active-controlled 8-week study with open label extension using medical device-grade subject worn sensors to measure waking and sleeping physical activity in the ambulatory outpatient setting. The 18 week study duration will consist of a 2-week baseline observation phase (with subjects continuing their current heart failure drug therapy), followed by an 8 week blinded treatment phase during which subjects are randomized (1:1) to either initiation of sacubitril/valsartan treatment or enalapril comparator, and finally an 8 week open label extension phase during which all subjects are treated with sacubitril/valsartan. Each subject will undergo a 36 hour washout period [during which ACEi (Angiotensin converting enzyme inhibitor), or study drug will be withheld] before the start of the randomized, blinded treatment phase, and again before beginning the open label extension phase. The study will include 8 office visits and 5 tele-visits.

Subjects will wear a wrist-worn actigraphy device continuously for the 18 week duration of the study, from the time of enrollment (the start of the 2 week baseline phase) to the end of the open-label extension phase (end of treatment week 16). During this 18 week interval, the devices will be exchanged five times during five study visits, to guard against data loss and ensure adequate battery life. Data will be collected continuously during the trial and although only data collected during assessment periods will contribute to prospectively defined endpoints, other data may be assessed in future analysis of patterns observed during the study. Additionally, continuous wear reduces opportunities for lapses in compliance while adding very minimal assessment burden for subjects.

Each assessment period is seven contiguous days. This will allow for continuous actigraphy recording over the seven day period.

**Figure 3-1** Study design

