- concomitant medication or non-drug therapy given
- non-drug therapy given
- patient hospitalized/patient's hospitalization prolonged (see [Section 7.2](#) for definition of SAE)
- its outcome (not recovered/not resolved; recovered/resolved; recovering/resolving, recovered/resolved with sequelae; fatal; or unknown)

Once an adverse event is detected, it must be followed until its resolution or until it is judged to be permanent, and assessment must be made at each visit (or more frequently, if necessary) of any changes in severity, the suspected relationship to the study drug, the interventions required to treat it, and the outcome.

Information about common side effects already known about the investigational drug can be found in the Investigator Brochure (IB). This information will be included in the subject informed consent and should be discussed with the subject during the study as needed. Any new information regarding the safety profile of the medicinal product that is identified between IB updates will be communicated as appropriate, for example, via an Investigator Notification or an Aggregate Safety Finding. New information might require an update to the informed consent and has then to be discussed with the subject.

The investigator must also instruct each subject to report any new adverse event (beyond the protocol observation period) that the subject, or the subject's personal physician, believes might reasonably be related to study treatment. This information must be recorded in the investigator's source documents; however, if the AE meets the criteria of an SAE, it must be reported to Novartis.

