### **9.5.2 Safety variables**

The safety and tolerability assessments are listed below:

- AEs and SAEs
- Sitting systolic, diastolic BP, and pulse pressure
- Heart rate
- Laboratory values

The assessment of safety will be based primarily on the frequency of adverse events, SAEs, and laboratory abnormalities. Other safety data will be summarized as appropriate.

The incidence of treatment-emergent adverse events (new or worsened) will be summarized by primary system organ class, preferred term, severity, and relationship to study drug. In addition, the incidence of death, SAEs, and AEs leading to discontinuation will be summarized separately by primary system organ class and preferred term.

Laboratory data will be summarized by presenting shift tables using extended reference ranges (baseline to most extreme post-baseline value), by presenting summary statistics of raw data and change from baseline values (mean, median, standard deviation, 25th and 75th percentiles, interquartile range, minimum and maximum) and by the flagging of notable values in data listings.

Data from other tests will be listed, notable values will be flagged, and any other information collected will be listed as appropriate.

Safety analyses will be performed based on the Safety Set. There will be no inferential analyses of the safety data.

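### The SAP's start-date definition of a treatment-emergent AE leaves out worsened events that the protocol counts, and the SAP text supplied declares no change

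*SAP*

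**What the plan says.** Protocol 9.5.2 (Safety variables) sets the analysis: "The incidence of treatment-emergent adverse events (new or worsened) will be summarized by primary system organ class", and then by preferred term, severity and relationship to study drug. Worsening is part of the definition.

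SAP 2.8.1.2 limits the AE summaries to treatment-emergent events and gives its own rule: "TEAEs are defined as AEs starting on or after the first day of study treatment". It then says what happens to the rest: "AEs starting prior to the first day of study treatment (non-TEAEs) will be flagged in the listings". The same section has a rule on severity: "A patient with multiple severities for an AE will be summarized under the worst severity recorded for the event".

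Three other places matter:

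- Protocol 7.1 counts AEs from written consent onwards and requires that each be tracked: "Once an adverse event is detected, it must be followed until its resolution or until it is judged to be permanent". Changes in its severity are to be assessed at each visit.
- Protocol 3.1 fixes the time between consent and first dose: "The 18 week study duration will consist of a 2-week baseline observation phase". A 36-hour washout also comes before blinded treatment.
- SAP section 1 presents the SAP as the detailed account of the protocol's planned analyses. SAP section 4, the place for changes to those analyses, shows no entry in the text supplied.

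**The concern.** The two documents give different membership rules for the same set of events, and the SAP is the one that will be programmed. An AE that begins in the baseline fortnight or the washout and becomes more severe on study drug keeps its early start date if it stays on one record. It is then a non-TEAE however severe it becomes. It would be missing from the tables by system organ class, severity, relatedness, seriousness and discontinuation.

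Protocol 9.5.2 rests the safety assessment primarily on the frequencies of AEs, SAEs and laboratory abnormalities, so the membership rule for the AE tables matters. Randomisation should balance the pool of pre-dose AEs between arms on average. Whether such an AE then worsens may depend on the drug received, so the omission need not cancel in the comparison.

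**Working it through.** No arithmetic applies: neither document gives a rate or a count for this point. The check compares definitions.

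**Step 1. Classify each kind of event under both rules.**

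| Event | Protocol 9.5.2 | SAP 2.8.1.2 |
|---|---|---|
| A. AE first starts on or after the first day of treatment | Counted | Counted |
| B. AE starts between consent and first dose and does not worsen | Not counted | Not counted |
| C. AE starts between consent and first dose and worsens on treatment, same record | Counted | Not counted |
| D. As C, but the worsening is entered as a new AE record with its own start date | Counted | Counted |
| E. Condition present before consent (medical history) that worsens on treatment and is reported as an AE | Counted | Normally counted, because the AE starts on treatment |

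Only row C differs.

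**Step 2. Look for anything in the SAP that brings row C back.**

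- The phase definitions in SAP 2.1.1 are date intervals and do not mention worsening.
- The AE date imputation in SAP 5.1.2 applies only to partial dates.
- The table list in 2.8.1.3 and the angioedema AE summaries in 2.8.1.4 add no definition of their own, so they take the rule in 2.8.1.2.
- Section 4 declares no narrower definition in the text supplied.

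Nothing restores the worsening criterion.

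**Step 3. Ask whether row C can occur.** It needs a period in which an AE can start before the first dose, and a recording practice that keeps a worsening on the same record.

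- The period exists. AEs are collected from consent, and the baseline phase (about 14 days) and the 36-hour washout come before the first dose. Protocol 6.6.4 allows the baseline phase to be repeated for poor device wear, which lengthens the period.
- On recording, protocol 7.1 follows the same AE for changes in severity, and protocol 7.2.2 treats progression of an SAE as follow-up to the event already reported. Neither document tells sites to open a new AE record when severity rises.

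Row C is therefore possible under the documents and is handled differently by the two definitions.

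**The case against.** The strongest reply is that worsening may be entered as a new AE (row D), in which case the start-date rule already captures it. There is support for this. Protocol 7.1 lists severity as a single item for each AE. The SAE definition in protocol 7.2.1 treats worsening of an existing condition as an event in itself. The SAP sentence on several severities can be read as a patient-level counting rule over several records of one term. The eCRF completion rules, which would settle the matter, are not among the documents. So it stands that nobody can say from the documents that events will certainly be lost. It does not stand that the gap is closed: the follow-up rules in protocol 7.1 and 7.2.2 lean towards one record, and the SAP does not say which practice it relies on.

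The second reply is that other outputs cover much of the loss, and this largely stands. All AEs are listed, with pre-dose ones flagged. Deaths have their own summary on the Full Analysis Set (SAP 2.8.2), and angioedema assessments have theirs (2.8.4.3). For the main risks named in protocol 3.6 (renal dysfunction, hyperkalemia and hypotension), the SAP also plans:

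- laboratory shift tables and notable creatinine and potassium changes (2.8.3, 5.3.2);
- notable blood pressure values (2.8.4.1, 5.4.1);
- reasons for not reaching Dose Level 3 (2.3.1);
- down-titrations by visit (2.4.1).

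A reader might infer that worsening on these risks would go unseen. The documents do not support that. What the other outputs do not replace is the AE tabulation itself: severity, relatedness and seriousness by preferred term.

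**Conclusion.** The mismatch between protocol 9.5.2 and SAP 2.8.1.2 is certain and, in the text supplied, undeclared. Its effect is confined to AEs that first start between consent and first dose, worsen on treatment, and stay on their existing record. Those events drop out of the tables in SAP 2.8.1.3 and 2.8.1.4 but not out of the listings.

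Two stronger readings should be resisted:

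- A reader might infer that worsening of any pre-existing problem is lost. Under protocol 6.2 and 6.5.1, conditions present before consent go into medical history. If one worsens on drug and is reported as an AE, it would normally carry an on-treatment start date and be counted.
- A reader might want to attach a number of patients. The documents give no rate of AEs before the first dose and none for their later worsening, so any figure would be a guess.

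The conclusion assumes that at least some worsenings are kept on the existing record. If the eCRF rules always require a new record, the tables will be right and only the wording needs aligning. This is a correction worth making before the AE tables are programmed. It affects the safety tables and leaves the efficacy analysis untouched.

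**What to change.** Replace the definition in SAP 2.8.1.2 with: *TEAEs are AEs that start on or after the first dose of study treatment, or that start before it and increase in severity on or after it.*

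Add that a worsened event is assigned to the treatment phase in which it worsened. The date to use is the recorded date of the severity change or, where a worsening is entered as a new AE record, that record's start date.

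The cost is one definition, one phase rule and a small amount of programming, on condition that the AE data carry a date of worsening. The documents do not show that they do, so check the data collection tool first. If no such date is collected, keep the start-date rule but state the narrower definition and its reason in SAP section 4, so that the departure from protocol 9.5.2 is on record.

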2.8.1.3 AE summaries

The following summary tables will be provided:

- AEs, regardless of study treatment relationship, by primary SOC, PT and worst severity
- Most frequent ($\geq 5\%$) AEs, regardless of study treatment relationship, by PT
- AEs suspected to be related to study treatment by primary SOC and PT
- Serious adverse events (SAE), regardless of study treatment relationship, by primary SOC and PT
- SAEs suspected to be related to study treatment by primary SOC and PT
- AEs leading to discontinuation, regardless of study treatment relationship, by primary SOC and PT
- AEs requiring dose adjustment or study treatment interruption, regardless of study treatment relationship, by primary SOC and PT
- AEs requiring additional therapy, regardless of study treatment relationship, by primary SOC and PT
- Death resulting from AEs by primary SOC and PT

2.8.1.4 Adverse events of special interest / grouping of AEs

Separate summaries will be provided for AEs related to angioedema, regardless of study treatment relationship. The summaries will be presented by primary SOC, PT and worst severity.

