### **3.6 Risks and benefits**

The risk to subjects in this trial will be minimized by compliance with the eligibility criteria and study procedures, close clinical monitoring, and the provision of rescue options.

Experience in the PARADIGM-HF trial; both in the run-in phase as well as the double-blind randomization phase indicated that the major risks associated with the treatment of sacubitril/valsartan are renal dysfunction, hyperkalemia, and hypotension. Results from the TITRATION study indicated that subjects whom are ACEi or ARB naïve are at an increased risk of experiencing these adverse events.

In this study, the risk of experiencing renal dysfunction, hyperkalemia, and hypotension are mitigated in this study by appropriate up-titration of the drug at weeks 2, 4, 8, 10, and 12. The risks are further mitigated by appropriate inclusion and exclusion criteria. Subjects are excluded if they have a potassium > 5.2 mmol/l at screening.

Sacubitril/valsartan may also cause angioedema. The risk of developing angioedema is increased if subjects take both an ACEi and sacubitril/valsartan. To decrease this risk, all subjects will undergo a 36 hour wash out period before entering the randomized phase epoch and before continuing into the open-label treatment epoch to minimize the interaction between an ACEi and sacubitril/valsartan in potentiating the development of angioedema.

All subjects will be allowed to continue receiving the rest of their background cardiovascular (CV) medications throughout the study. Subjects will be randomized to study treatment only after the investigator has confirmed the subject is on stable treatment with guideline-directed therapy for heart failure with reduced ejection fraction (HFrEF), other than ACEis and ARBs, which will ensure that subjects are receiving appropriate treatment for their heart failure.

In the PARADIGM-HF study, sacubitril/valsartan reduced the risk of cardiovascular (CV) death, HF hospitalization and due to these significant results, sacubitril/valsartan is now indicated to reduce these risks in subjects with chronic heart failure (NYHA class II-IV) and reduced ejection fraction.

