### **5.5.5 Permitted dose adjustments and interruptions of study treatment**

Every attempt should be made to maintain subjects on the target study drug dose level for as long as possible throughout the study. If, however, in the opinion of the investigator, a subject is unable to tolerate the protocol-specified target dose, the investigator should consider whether dose adjustments of concomitant medications may rectify the situation before reducing the dose of study treatment. If adjustment of the concomitant medications is not possible or does not alleviate the side effects of concern, the investigator may down-titrate the dose of the study drug to the previous dose level. If needed, the study drug may be stopped completely, if this occurs, the subject should return to the clinic as soon as possible, after discontinuation of study drug, for an end of study visit. Subjects may restart their current dose of study drug following an interruption of treatment, based on investigator judgment.

Study drug dose level adjustments should be mainly based on overall safety and tolerability with special focus on:

- Hyperkalemia
- Symptomatic hypotension
- Clinically significant decrease in eGFR/increase in serum creatinine (defined as a serum creatinine of  $\geq 0.5\text{mg/dl}$  with at least a 25% decrease in eGFR).

These changes must be recorded on the Dosage Administration Record CRF.

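### The SAP groups adverse events for angioedema only, so no pooled, once-per-patient AE incidence is planned for hypotension, hyperkalemia or renal dysfunction, the three risks the protocol calls major

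*SAP*

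**What the plan says.** Protocol 3.6 (Risks and benefits) states that "the major risks associated with the treatment of sacubitril/valsartan are renal dysfunction, hyperkalemia, and hypotension", and then adds angioedema as a further risk. Protocol 5.5.5 repeats the emphasis: "Study drug dose level adjustments should be mainly based on overall safety and tolerability with special focus on" hyperkalemia, symptomatic hypotension, and a clinically significant fall in eGFR or rise in creatinine. Protocol 9.5.2 sets the basis of the safety evaluation: "The assessment of safety will be based primarily on the frequency of adverse events, SAEs, and laboratory abnormalities".

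SAP 2.8.1.4, the section for events of special interest and AE grouping, has one entry: "Separate summaries will be provided for AEs related to angioedema, regardless of study treatment relationship". These summaries run by primary SOC, PT and worst severity.

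The other AE tables follow SAP 2.8.1.2, which counts patients with any treatment-emergent AE, those "having at least one TEAE in each primary SOC, and for each PT using MedDRA terminology". In SAP 2.8.1.3 the first table is "AEs, regardless of study treatment relationship, by primary SOC, PT and worst severity", with no frequency cut-off. The second is "Most frequent ($\geq 5\%$) AEs, regardless of study treatment relationship, by PT". The SAP does not say whether the 5% applies within an arm, in either arm, or to all patients.

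**The concern.** The protocol singles out three risks, but the SAP section meant for grouped events carries only the fourth. The SAP itself lists all four side by side in 2.3.1, as reasons for not achieving dose level 3, so the omission from 2.8.1.4 does not follow from the SAP's own classification.

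If one risk is recorded under several PTs, the PT counts cannot be added afterwards from the tables, because a patient may have more than one. A risk spread over several infrequent PTs can also be absent from the 5% table. Protocol 9.5.2 and SAP 2.8 plan no inferential safety analysis, so descriptive incidence carries the safety comparison with enalapril. A grouping chosen after unblinding would be made with the arms known.

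**Working it through.** **Inputs.** SAP 1.1 gives about 136 patients randomized 1:1, so 68 per arm; Protocol Table 5-1 also shows 68. The Safety Set is the denominator (SAP 2.8) and is at most about this size. The cut-off is 5% by PT (SAP 2.8.1.3). The documents give no expected AE rates and no PT lists, so the total rate and the number of PTs per risk are assumptions, shown as ranges. The plan states no figure of its own on this point to reproduce.

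**Step 1: patients needed to enter the 5% table.** 0.05 × 68 = 3.4, so a PT needs 4 patients (4/68 = 5.9%). A PT with 3 (3/68 = 4.4%) is left out. If the cut-off applies to all 136, 0.05 × 136 = 6.8, so 7 are needed.

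**Step 2: largest total that can be hidden.** With k PTs, 3 different patients in each, the hidden total is 3k/68:
- k = 2: 6/68 = 8.8%
- k = 3: 9/68 = 13.2%
- k = 4: 12/68 = 17.6%

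On the all-patient reading the hidden totals are 12, 18 and 24 of 136, the same percentages.

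**Step 3: how likely this is.** Assume a total rate p in one arm of 68, with each affected patient under exactly one of k equally likely PTs. The counts are then multinomial. P(every PT ≤ 3) is the chance that the risk is missing from the 5% table; P(total ≥ 4) is the chance that a pooled count would reach 5%.

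| p | 2 PTs | 3 PTs | 4 PTs | pooled count ≥ 4 |
|---|---|---|---|---|
| 8% | 50% | 71% | 82% | 80% |
| 10% | 30% | 52% | 68% | 92% |
| 12% | 16% | 35% | 52% | 97% |
| 15% | 5% | 16% | 30% | 99% |

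A 70/15/15 split over three PTs gives about 28% at p = 10% and 5% at p = 15%. If the risk codes to one PT, the PT count is the pooled count and nothing is lost.

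**Step 4: effect of the unstated denominator (p = 10% in both arms, equal split).** If a PT is shown when it reaches 5% in either arm, the chance that none shows is the one-arm value squared: 0.52² = 27% for 3 PTs and 0.68² = 46% for 4. If 5% applies to all 136, it is about 57% and 79%.

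**Step 5: do other planned tables give the pooled incidence?**
- SOC totals (SAP 2.8.1.2) count each patient once but mix in unrelated events.
- The uncut table (SAP 2.8.1.3) shows every PT, but PTs cannot be summed over patients.
- Dose-level-3 reasons (SAP 2.3.1) are pooled by risk, but only for patients who did not reach level 3. A patient who reached it and later had an event is not counted.
- Notable low systolic pressure (SAP 5.4.1) needs both a value below 90 mmHg and a fall of more than 20 mmHg. Exclusion 3 admits 95 mmHg at randomization; from that baseline only a value below 75 counts (95 − 20 = 75). Symptoms are not captured.
- Notable potassium (SAP 5.3.2) is a change above 20%. A rise from 4.8 to 5.7 mEq/L is 0.9/4.8 = 18.75% and is not flagged, though it exceeds the 5.3 in Protocol Table 5-7. A rise from 4.0 to 4.9 is 22.5% and is flagged, though it stays below 5.3.
- Notable creatinine (SAP 5.3.2) is an increase above 50%, and eGFR is not on that list, whereas Table 5-7 refers to eGFR falls of 25% and 35%.
- Laboratory shift tables (SAP 2.8.3) give low, normal or high only.

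**The case against.** A reader might infer that the three risks are counted only by single PT, or that their events disappear from the report. The documents do not support that. The SOC totals, the dose-level-3 reasons, and the laboratory and blood pressure tables all bear on these risks. The 5% table is one of nine AE tables, the first has no cut-off, and all AEs are listed, so a once-per-patient count could still be made later. What is missing is the pre-specified grouping and its table, not the data.

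A reader might also infer that the plan lacks its main tolerability result. That overstates it: the visible Table 2-1 has no safety or tolerability objective, and tolerance of titration is addressed by the dose-level-3 reasons and the titration summaries in SAP 2.4.1. For potassium and renal function, central laboratory values at six visits (Protocol 6.5.5.2) are arguably more complete than AE reports, since under Protocol 7.1 an abnormal value is an AE only if symptomatic, clinically significant or treated.

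The probabilities are also open to challenge. They rest on assumed rates and on one PT per patient; overlap or an uneven split lowers the chance of omission. Protocol 6.5.5 asks for the diagnosis or condition to be entered when a laboratory abnormality causes symptoms or needs intervention, which works against scatter over PTs. The table shells were not available and parts of the SAP are redacted, so a grouping defined there cannot be excluded, although 2.8.1.4 itself reads complete.

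All of this stands, and it limits the severity. It does not supply the missing figure: none of the tables cited is a pooled AE incidence.

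**Conclusion.** The point holds as a minor one. In the visible plan only angioedema has an AE grouping, and no once-per-patient AE incidence is planned for hypotension, hyperkalemia or renal dysfunction. At 68 per arm the by-PT 5% table can leave out a risk affecting up to 13.2% of an arm if it is spread over three PTs. At an assumed 10% total rate without overlap, the chance of omission in one arm runs from about 28% (70/15/15 split) or 30% (two equal PTs) to 68% (four equal PTs). How events will actually divide over PTs cannot be known from the documents. No alpha, power or sample size figure is affected.

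**What to change.** Add three groupings to SAP 2.8.1.4: hypotension, hyperkalemia and renal dysfunction. Define each by a standardised MedDRA query or a listed set of PTs, fixed before unblinding. Summarize each by arm, treatment phase and worst severity, counting each patient once per group. Show these groups whatever the 5% cut-off, and state in 2.8.1.3 whether the 5% rule applies in either arm or overall. If the table shells already contain such groupings, refer to them in 2.8.1.4.

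The cost is a term list and three tables from data that will be coded anyway. No new data are needed and no clinical rule changes.
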